10.2. Sample Size Determination

In order to ensure adequate exposure for evaluation of safety, the study is designed with a target of 140 participants to be randomized into the combination arm. At least 280 participants will be randomised in this study, with a target of 70 participants in Arm A, 140 participants in Arm B and 70 participants in Arm C. This sample size provides at least 98% power (for the comparison of Arm B to Arm A at Week 52) at the 5% level of significance assuming the underlying response in the control arm is 10% and the true population effect is ≥25% with treatment Arm B (combination assumed response rate of 35%). The primary endpoint will be based on assuming study dropouts = treatment failures, and so the assumed responder rates for treatment Arms A and B already account for participant dropout rates. However, the sample size may be increased up to a maximum of 320 participants if the dropout rate, missing data or number of major protocol deviations suggests further participants are necessary to ensure robust conclusions can be drawn. Sample size was calculated using PASS 12 and is based in the Likelihood ratio test. No inferential tests are planned between Arm C and Arm A or Arm B; therefore no adjustment for multiplicity is required.

There are limited clinical data with therapies including both belimumab and rituximab. Based on elicitation of opinion from external experts, as well as the rarity of remission or disease control seen in published external studies and internal GSK review of previous belimumab data, a rate of 35% achieving a state of disease control (i.e., Arm B) is considered to be highly significant in SLE care. The assumed 10% responder rate in Arm A (control) at 52 weeks was estimated based on exploration of historical data from three comparable belimumab Phase 3 trials (IV: C1056 [BLISS-76] and C1057 [BLISS-52] and SC: BEL112341) in patients with SLE, albeit with some significant differences from this study in protocol inclusion criteria, control of background therapy for SLE, SLEDAI-2K derivation and treatment failure rules. The estimated Arm A

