(control) response rates based on data from previous belimumab Phase 3 studies ranged from 3.3% (C1056), 7.3% (C1057), and 8.3% (BEL112341). It is appreciated that these rates are derived from studies that did not include a forced steroid or immunosuppressant taper. Due to the limitations of the historical data and therefore the likely imprecision of the estimated responder rates, a more conservative estimate of the assumed belimumab monotherapy arm of 10% is being used for sample size calculations.

Assuming a 10% control responder rate and 70 participants in Arm A and 140 participants in Arm B, the minimum detectable effect (MDE) at p-value <0.05 is a 11% improvement (i.e., an observed improvement with the combination of 11% or more would give a p-value <0.05).

Sample Size Sensitivity

A sample size sensitivity analysis was conducted on the primary endpoint, to investigate the impact on power if the assumed underlying control response rate deviates from 10% or the treatment difference deviates from 25%. The results of these analyses are displayed in Table 5.

Table 5 Power if the Underlying Response Rates Vary from 10% (Control) and 35% (Combination)^a

Control Rate (Arm A)	Combination Rate (Arm B)	Power
5%	30%	99%
15%	40%	97%
10%	25%	75%
10%	30%	93%
10%	40%	99%

a. All calculations assume a 5% level of significance, N=70 (control), N=140 (combination).

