10.4.1. Efficacy Analyses

Unless otherwise stated, the primary and key secondary efficacy endpoints will be conducted using the:

- MITT population
- Blinded independent assessors SLEDAI-2K data

Endpoint	Statistical Analysis Methods
Primary	Endpoint: The proportion of participants with a state of disease control defined as a SLEDAI 2K-score ≤2, achieved without immunosuppressants and with corticosteroids at a prednisone equivalent dose of ≤5mg/day at Week 52. (Arm B: combination vs Arm A control)
	Analysis: The proportion of subjects achieving a treatment response (as defined for the primary endpoint) at Week 52 will be compared between Arm B (combination) vs Arm A (control) using a logistic regression model. The independent variables in the model will include treatment group, baseline SLEDAI-2K score (≤9 vs. ≥10 mg/day), immunosuppressant use at baseline (immunosuppressant use vs. no use), and baseline corticosteroid dose

Endpoint	Statistical Analysis Methods	
	(prednisone equivalent ≤10 mg/day vs. ≥10 mg/day). If any factor fails to converge it will be removed from the logistic model. If the logistic model fails to converge, e.g., due to a small number of responders, the primary endpoint will be analyzed using a Fishers exact test.	
	Missing data for the primary endpoint will be handled as follows:	
	• The study is designed to continue to collect data for participants who prematurely discontinue from their randomized treatment. All data on the primary endpoint collected for these participants will be included in the primary analysis, irrespective of whether they are classified as 'on-treatment' or not. For participants who withdraw prematurely from study treatment and for whom subsequent collection of data is not possible, it will be assumed for the primary analysis that they are treatment failures. A dropout/treatment failure = non-responder (DO/TF=NR) analysis will be used, therefore no missing data will be assumed as all participants will be classed as either a non-responder or responder. The basic premise of the DO/TF=NR analysis is that a participant meeting any of treatment failure criteria defined below (prior to Week 52), will be considered a treatment failure and thus counted as a non-responder in the statistical analysis:	

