2.4. Statistical Hypotheses / Statistical Analyses

The primary objective of the study is to demonstrate superiority (improvement in response rate) of co-administration of belimumab plus rituximab (Arm B: Combination) over belimumab monotherapy (Arm A: Control), when comparing the primary efficacy endpoint at Week 52 in subjects with SLE.

Analysis of the primary objective will use data from the whole population and therefore includes subjects from treatment Arms A, B, and C, even though the primary objective is only comparing treatment Arms A and B. Hence an exploratory assessment of the relative performance of Arm A (Control) and Arm B (Combination) vs. standard SLE therapy (Arm C: Reference) will also be conducted using the same analysis.

The primary efficacy endpoint is defined as: the proportion of participants with a state of disease control defined as a SLEDAI-2K score (IBA) ≤ 2 , achieved without immunosuppressants and with corticosteroids at a prednisone equivalent dose of ≤ 5 mg/day at Week 52.

- Null Hypothesis (H₀):** There is no difference between Arm B (combination) and Arm A (control) in terms of the primary endpoint at Week 52.
- Alternative Hypothesis (H₁):** There is a difference between Arm B (combination) and Arm A (control) in terms of the primary endpoint at Week 52.

A step-down sequential testing procedure will be used to control the overall type 1 error rate for comparing Arm B (combination) vs Arm A (control). With this procedure, the primary endpoint and the two major secondary endpoints will be evaluated for statistical significance based on a pre-specified sequence for interpretation (i.e., disease control at Week 52, followed by clinical remission at Week 64 and then disease control at Week 104, see [Figure 1](#)). Specifically, endpoints will be tested in the sequence above (2-sided alpha=0.05) provided that statistical significance is achieved by all prior tests. If at any point in the sequence statistical significance is not met, then subsequent endpoints in the sequence cannot be deemed statistically significant. Analyses of other efficacy endpoints will not be subject to any multiple comparison procedure.

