7.1.5. Statistical Analyses / Methods

7.1.5.1. Statistical Methodology Specification

| |
|---|
| Endpoint / Variables |
| 
 The proportion of participants with a state of disease control defined as a SLEDAI-2K score ≤ 2 (IBA), achieved without treatment failure or study withdrawal |
| Derivation |
| 
 Derivation of the endpoint for Arms A, B and C is provided in Section 15 |
| Model Specification |
| 
 Logistic regression model. Terms in the model: 
 Dependent: response (yes/no) Categorical: treatment group, baseline SLEDAI-2K score (≤ 9 vs. ≥ 10), baseline immunosuppressant use (use vs. non-use), and baseline corticosteroid dose (prednisone equivalent ≤ 10 mg/day vs. > 10 mg/day). |
| Model Checking & Diagnostics |
| 
 If any factor fails to converge it will be removed from the logistic model. If the logistic model fails to converge, e.g., due to a small number of responders, the primary endpoint will be analyzed using a Fishers exact test. If the model diagnostics raise questions about the validity of the analysis additional non-parametric analysis will also be conducted. |
| Model Results Presentation |
| 
 The table [T12.01] will display: 
 the number, percentage, SE of percentage, and the 95% CI for the percentage of subjects achieving a response by treatment group, the observed difference in percentage of responders for the comparison of Arm B vs Arm A; and Arm B vs Arm C, the stratified (baseline SLEDAI-2K score, baseline immunosuppressant use, baseline corticosteroid dose) Cochran-Mantel-Haenszel treatment difference and 95% confidence interval (CI) for the comparison of Arm B vs Arm A; and Arm B vs Arm C. the odds ratio and 95% confidence interval (CI) for the comparison of Arm B vs Arm A; and Arm B vs Arm C. the p-value for the odds ratio the treatment difference for Arm B vs Arm A. A table [T12.02]. showing the details from the logistic regression will also be presented; including: 
 the parameter estimate and standard error for each of the terms in the model the odds ratio and 95% CI and p-value for each covariate in the model the parameter estimate, standard error, odds ratio, 95% CI and p-value for the comparison of Arm B vs Arm A |

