7.2.5. Statistical Analyses / Methods

7.2.5.1. Statistical Methodology Specification

| |
|---|
| Endpoint / Variables |
| 
 The proportion of participants with a state of clinical remission defined as a Clinical SLEDAI-2K score = 0 (IBA), achieved without immunosuppressants and with corticosteroids at a prednisone equivalent dose of 0 mg/day at Week 64, and without treatment failure or study withdrawal |
| Model Specification |
| 
 The proposed statistical analyses planned for the primary endpoint will be repeated for this major secondary endpoint. |
| Model Checking & Diagnostics |
| 
 The model and diagnostics checks proposed for the primary endpoint will be repeated for this major secondary endpoint. |

| |
|--|
| Model Results Presentation |
| 
 The proposed tables and figure for the primary endpoint will be repeated for this major secondary endpoint [T22.01, T22.02, F22.01]. |
| Subgroup Analyses |
| 
 Subgroup analyses will not be conducted for major secondary endpoints. |
| Supportive Analyses |

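### With few responders, the fallback lets the outcome data choose covariates and test; a pre-specified Firth refit is cleaner, for a small power gain

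*SAP*

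**What the plan says.** The planned analysis (SAP 7.1.5.1, Protocol 10.4.1) is a logistic regression of response on treatment group and three two-level baseline factors: SLEDAI-2K score, immunosuppressant use and corticosteroid dose. Two contingency rules follow.

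- For a single factor: "If any factor fails to converge it will be removed from the logistic model".
- If the model as a whole does not converge, for which a small number of responders is the example given, "the primary endpoint will be analyzed using a Fishers exact test" (Protocol 10.4.1, repeated in the SAP).

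SAP 7.2.5.1 carries both rules to the Week 64 endpoint: "The model and diagnostics checks proposed for the primary endpoint will be repeated for this major secondary endpoint". SAP 7.3.5.1 does the same for Week 104. The tests run in the order Week 52, Week 64, Week 104, each at two-sided 0.05 and only if the one before is significant (SAP 2.4 and 5.6).

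Three other points bear on this:

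- The results tables carry a Cochran-Mantel-Haenszel difference and 95% CI stratified on all three factors, but the p-value is the one for the odds ratio.
- The sample size in Protocol 10.2 rests on a likelihood-ratio test. Neither document says whether the logistic p-value is Wald or likelihood-ratio.
- No response rate or power is given for Week 64.

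**The concern.** Maximum-likelihood logistic regression has no finite solution when one level of a term has no responders (separation). Sparse data at Week 64 are plausible from the documents. That endpoint needs a clinical score of 0 on 0 mg/day of steroid. The recommended final taper from 5 mg/day starts at Week 26 and takes 35 weeks (Protocol Appendix 2), so it ends at about Week 26 + 35 = 61.

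If the group above 10 mg/day at baseline had no responders, the rule would remove that factor. If Arm A had none, the treatment odds ratio itself could not be estimated and Fisher's test would take over, ignoring all three factors. Either way, the model behind the p-value is settled after the outcomes are seen.

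The rule is also hard to execute. Models converge or fail; single factors do not. The documents do not say how the offending factor is identified, whether the model is refitted before moving to Fisher's test, or what happens when treatment is the separated term. At stake is the Week 64 test and, through the gate, the Week 104 test.

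**Working it through.** **Stated figure.** Protocol 10.2: "This sample size provides at least 98% power", for 10% vs 35%, N = 70 and 140, two-sided 5%. The pooled rate is (70×0.10 + 140×0.35)/210 = 0.2667. Then z = [0.25 − 1.96·√(0.2667×0.7333×(1/70 + 1/140))] / √(0.10×0.90/70 + 0.35×0.65/140) = (0.25 − 0.1269)/0.05395 = 2.28, so power is 98.9%. Exact enumeration gives 99.0% (likelihood ratio), 98.9% (Pearson) and 98.7% (Fisher). The stated figure reproduces, and even Fisher's test costs nothing that matters at the planned Week 52 rates.

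**How often Arm A has no responders.** (1 − p)^70 is 24% at p = 2%, 12% at 3%, 3% at 5% and 0.1% at 10%.

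**What the choice of test does, without covariates.** Exact power at an assumed 3% vs 13% is 75.1% (likelihood ratio), 70.2% (Pearson), 65.3% (Fisher) and 50.1% (Wald). With 0/70 vs 8/140, Fisher gives p = 0.054 and the likelihood ratio p = 0.010. Fisher's test is conservative here, but the Wald test is weaker still.

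**Simulation of the plan against the repair.** The plan drops a factor that has an empty level and uses Fisher's test if an arm has no responders. The repair uses Firth's penalised likelihood with all three factors, only when the plan's fallback would fire. Sample sizes are from Protocol 10.2. Everything else is assumed: 45% of patients above 10 mg/day, prevalences of 50% and 60% for the other two factors with no effect, and 1,500 trials per scenario (Monte Carlo SE about 1.3 points). P-values outside the fallback are Wald.

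| Rates (A vs B), steroid OR | Fallback fires | Plan | Repair | Gain |
|---|---|---|---|---|
| 3% vs 12.6%, 0.1 | 26.4% (14.7% factor dropped, 11.7% Fisher) | 59.2% | 61.1% | 1.9 |
| 2% vs 11.7%, 0.1 | 38.6% | 67.8% | 71.0% | 3.2 |
| 3% vs 12.6%, 0.02 | not tabulated | 59.6% | 68.1% | 8.5 |
| 3% vs 12.6%, 0.33 | factor dropped in 0.8% | 59.1% | 59.3% | 0.2 |
| 10% vs 23%, 0.1 | about 2% | 68.9% | 69.0% | 0.1 |

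The gain when the fallback fires is 1.9/0.264 = 7.2 points in the first row and 3.2/0.386 = 8.3 in the second.

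**Same fallback, likelihood-ratio p-values.** Power is 72.7% and 81.7% in the first two rows. Adding the Firth refit changes this by −0.6 and −0.8 points.

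**Limiting case.** If no patient above 10 mg/day responds (40% in that group, the other two factors with OR 0.6), the fallback fires in over 99% of trials:

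| Rates | Factor dropped, Wald | Factor dropped, likelihood ratio | Firth |
|---|---|---|---|
| 2% vs 10% | 47.9% | 68.0% | 63.2% |
| 5% vs 15% | 56.9% | 65.8% | 64.1% |
| 5% vs 20% | 85.9% | 89.1% | 90.5% |
| 10% vs 25% | 75.0% | 78.6% | 82.7% |

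Firth gains 5 to 15 points over Wald. Against the likelihood ratio it ranges from 4.8 points worse to 4.1 better.

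**Type I error.** With equal rates of 2-5% in both arms, the plan with Wald p-values rejects in 1-4% of trials and the repair in 2.9-4.6%. The likelihood-ratio version of the plan rejects in 2.9% (3% in both arms) and 5.2% (5% in both arms), the latter within simulation error of 5%.

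**The case against.** The strongest reply is that most of the lost power comes from the Wald statistic, which the SAP never specifies. The only test the documents name is the likelihood ratio, in the sample-size section. With it, the existing fallback does as well as the Firth refit or slightly better in the main scenarios. This stands, and it is why the p-value should be named.

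Other parts also stand:

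- The rule is pre-specified in both documents and does not inflate type I error.
- The stratified Cochran-Mantel-Haenszel difference and CI are reported regardless, so adjusted information is not lost.
- A Firth refit on separation also switches on the observed data. It keeps the four model terms fixed but does not remove the switch.
- The Week 64 rates and the steroid effect are assumptions. The 3.3% to 8.3% control rates in Protocol 10.2 are for Week 52. The Week 64 score omits serology, and SAP 7.2.1 notes that a patient may respond at Week 64 without having met the primary endpoint.

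A reader of the second SAP addendum might infer that the Week 52 gate was not passed, which would make formal Week 64 power moot. The addendum moves to abridged outputs but states no result, and it still lists the Week 64 and Week 104 logistic regressions.

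What the reply does not answer is that the trigger and the order of steps are undefined, and that the reported p-value could come from a model with fewer factors than the stratified difference shown beside it.

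**Conclusion.** The point holds as a matter of clarity and robustness, with a small cost in power. Under assumed low Week 64 rates, a strong steroid effect and Wald p-values, the fallback fires in about 26-39% of trials, and replacing it gains about 2-3 points overall. The gain is about 8 points if almost no patient above 10 mg/day responds, and larger only in the limiting case at the lowest rates. It is negligible with a moderate steroid effect, near Week 52 rates, or with likelihood-ratio p-values. Priority is low.

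Four stronger readings are tempting but not supported:

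- **A loss of about 7 to 9 points.** This comes from comparing the plan with Firth in every trial (66.5% vs 59.2%, 76.9% vs 67.8%), which is a different proposal from a refit on separation.
- **Dropping a factor leads on to Fisher's test.** The two have separate triggers. Once a factor is removed, the model normally converges unless an arm has no responders.
- **The dropped factor is the most prognostic one.** The documents give no association between steroid dose and response. An empty level can arise by chance: with no factor effect and 2% responding in both arms, some factor had one in 44% of simulated trials.
- **The primary test is at risk.** At the planned Week 52 rates, Fisher's test alone has 98.7% power.

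**What to change.** In SAP 7.1.5.1, and by reference in 7.2.5.1 and 7.3.5.1, replace both contingency rules with one:

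- Define the trigger as separation or non-convergence of the planned model, including separation on treatment.
- When it is met, fit the same model (treatment plus all three factors) by Firth penalised likelihood, and take the p-value and CI from the penalised profile likelihood.
- Report Fisher's test as a descriptive check only.
- State whether p-values are otherwise Wald or likelihood-ratio. The likelihood ratio matches the sample-size basis in Protocol 10.2 and recovers most of the lost power by itself.

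The cost is a change of wording and one software option, with Protocol 10.4.1 aligned. The estimate is shrunk slightly towards no effect. Compared with a likelihood-ratio version of the existing fallback, power would usually be less than 2 points lower where it is lower at all. The exception in these runs is 4.8 points, at 2% vs 10% when no patient above 10 mg/day responds.

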7.1.6. Tipping Point Analysis

Tipping point analyses will be performed for the primary endpoint if the endpoint is statistically significant and it is plausible that missing data caused by study withdrawal could alter the conclusions of the analysis (treatment p-value is ≤ 0.05 and > 0.001). If the tipping point analyses are needed, they will be performed shortly after the Statistical Analysis Complete milestone has been met and will be presented in the clinical study report.

The tipping point analyses will be based on the Intent-to-Treat population. Only the subjects in the belimumab plus placebo, and belimumab plus rituximab arms will be considered.

For the primary analysis, subjects for whom the Week 52 disease control status cannot be determined due to study withdrawal (including lost to follow-up, and death) are imputed as non-responders. In contrast, the missing data due to study withdrawal in the tipping point analysis is evaluated using multiple imputation methods, by simulating all combinations of response probability in the treatment arms independently.

The first tipping point analysis will use the Hybrid strategy (as described in Section 7.1.4 as per the primary estimand). If a subject's study withdrawal is subsequent to treatment failure the subject will still be considered as a non-responder, i.e. the non-responder assumption will only be varied for withdrawn subjects that were not treatment failures.

The second tipping point analysis will use the treatment policy strategy (Section 7.1.4). In this approach, treatment failure data is ignored, i.e. the non-responder assumption is varied for all withdrawn subjects regardless of treatment failures.

The tipping point analyses will not consider covariates. However, if the conclusions of the primary analysis adjusting for covariates differ from the conclusions of the unadjusted analysis, a post hoc analysis assessing the impact of covariate adjustment in the tipping point analyses may be performed.

[figure not shown]
The following multiple imputation method will be implemented:

1. For subjects in Arm A (belimumab plus placebo) and Arm B (belimumab plus rituximab) with missing Bernoulli outcomes, a grid of the probability of response varying from 0.025 to 0.975 by 0.025 will be created. This will create all combinations, from low to high response probability, for subjects with a missing response.
2. For a given of probability (e.g., 0.025 for Arm A, 0.500 for Arm B)
 - a. An incidence of the number of additional responders for Arm A (Arm B) given the number of Arm A (Arm B) subjects with missing outcome and the probability assumed (e.g., 0.025 (e.g., 0.500)) will be simulated using the binomial distribution.
 - b. The statistics (sample mean and standard error) will be calculated and used to construct the Mantel-Haenszel Chi-Square test.

Steps 2a and 2b will be repeated 1000 times, and Rubin's rules applied to combine them, in order to obtain a single p-value for each given probability combination.

Heat maps will be produced (Figure 2) to show the results of the multiple imputation tipping point analyses for disease control at Week 52. The black lines on each heat map will represent a plausible scenario whereby the probability of response for the missing data in Arms A and B will be equal to the observed case response rate on the control arm (Arm A: belimumab plus placebo).

Figure 2 Tipping Point for Disease Control at Week 52

A tipping point analysis will also be performed for the key secondary endpoints if there is hierarchical significance for the endpoint, and it is plausible that the imputation strategy for missing data could alter the conclusions of the analysis (treatment p-value is ≤ 0.05 and > 0.001).

7.1.7. Additional Analyses to Assess the Impact of the Coronavirus Disease 2019 (COVID-19) Pandemic on the Primary Endpoint

Additional analyses will be carried out to assess the impact of the COVID-19 pandemic on the primary endpoint. The additional analyses will utilise the COVID-19 environment onset date (Section 15.6.16) to establish which data might be affected by COVID-19.

7.1.7.1. COVID Attributed – Observed Data until Intercurrent Events That Could be Attributable to the COVID-19 Pandemic

The first additional analysis (T12.40) uses the observed SLEDAI-2K data, as long the subject has not experienced a treatment failure or study withdrawal that could have been attributable to COVID-19 (i.e. after the COVID-19 environment onset date).

A Hypothetical estimand will be used to estimate the treatment effect had the COVID-19 pandemic not occurred. The difference in response rates between Arm A and Arm B at Week 52 will be assessed for subjects who:

- achieve a SLEDAI 2K-score ≤ 2 (IBA),
- without immunosuppressants that could be attributable to the COVID-19 pandemic and
- with corticosteroids at a prednisone equivalent dose of $\leq 5\text{mg/day}$, in the absence of higher doses that could be attributable to the COVID-19 pandemic

The full MITT population will be used, with the following attributes:

- A strategy that matches the primary analysis (Hybrid) will be used for the following Intercurrent Events to classify the subject as a Non-Responder:
 - Study Withdrawal (includes Lost to Follow Up) that occurs prior to the COVID-19 environment onset date
 - Treatment Failure (includes consideration of corticosteroids and immunosuppressants) that occurs prior to the COVID-19 environment onset date
 - Death that occurs at any time
- A hypothetical strategy will be used for any subject who has their Week 52 assessment scheduled to be on or after the COVID-19 environment onset date, who has not been classified as a Non-Responder using the strategy above, and has any of the following Intercurrent Events on or after the COVID-19 onset date:
 - Study Withdrawal (includes Lost to Follow Up)
 - Treatment Failure (includes consideration of corticosteroids and immunosuppressants)
 - Missing SLEDAI-2K score (IBA)

The response status for these subjects will be treated as a missing value and will be assumed to be Missing At Random (MAR). It will be imputed using Multiple Imputation methods, which take into account the subjects baseline characteristics and their existing pre-COVID-19 data.
- Discontinuation of study investigational product (belimumab or rituximab) is NOT a component of this endpoint.

| |
|--|
| Imputation of Missing Data |
| 
 • A bayesian repeated measures logistic regression model will be fitted to the observed data, using a Markov Chain Monte Carlo (MCMC) approach, adjusting for treatment group, baseline SLEDAI-2K score (≤ 9 vs. ≥ 10), baseline immunosuppressant use (use vs. non-use), and baseline corticosteroid dose (prednisone equivalent ≤ 10 mg/day vs. >10 mg/day). Non-informative priors will be used. • Samples will be drawn from the posterior distribution of the model parameters of the Bernoulli distribution for each treatment group and each missingness pattern. • Each sample leads to a separate imputed dataset, in which the missing values are replaced by values drawn randomly from their conditional distribution. This distribution is based on the observed data and the covariates for that subject using the imputation model and the sampled parameter values. • These steps will be repeated at least 1000 times. |
| Model Specification |
| 
 • Each imputed dataset will be analyzed using logistic regression to evaluate the treatment effect controlling for treatment group, baseline SLEDAI-2K score (≤ 9 vs. ≥ 10), baseline immunosuppressant use (use vs. non-use), and baseline corticosteroid dose (prednisone equivalent ≤ 10 mg/day vs. >10 mg/day). • The resulting Odds Ratios and their Standard Errors will be combined across imputations using Rubin's rules. |

